12.2 Assessment of Adverse Event Severity and Relationship to Treatment

The AEs will be graded by severity utilizing CTC version 4.0. A copy of the criteria can be downloaded from the CTEP home page at <http://ctep.cancer.gov/reporting/ctc.html>. The category that overall best "fits" the relationship between the adverse event and the study drug should be chosen and recorded on the CRF and SAE form, if appropriate.

The investigator is responsible for assessing the causal relationship between any events and the study treatment. AEs will be attributed as unrelated, unlikely, possibly, probably, or definitely related to study medication or procedures. Additionally, the investigator is responsible for

providing appropriate treatment for the event and for adequately following the event until resolution.

Relationship Between Treatment and AE

Unrelated	No temporal association to study product. An alternate etiology has been established. The event does not follow the known pattern of response to study product. The event does not reappear or worsen with re-challenge.
Probably not related / remote	No temporal association to study product. Event could readily be produced by clinical state, environmental or other interventions. The event does not follow the known pattern of response to study product. The event does not reappear or worsen with re-challenge.
Possibly related	Reasonable temporal relationship to study product. The event is not readily produced by clinical state, environmental, or other interventions. The event follows a known pattern of response to the study product or as yet unknown pattern of response.
Probably related	There is a reasonable temporal association with the study product. The event is not readily produced by clinical state, environmental, or other interventions. The event follows a known pattern of response to the study product. The event decreases with de-challenge.
Definitely related	There is a reasonable temporal relationship to the study product. The event is not readily produced by clinical state, environmental, or other interventions. The event follows a known pattern of response to the study product. The event decreases with de-challenge and recurs with re-challenge.

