Further analysis of the study population revealed that CIS had a favorable safety profile, and long-term administration did not lead to exacerbations of known toxicities of oral and intravenous cyclosporine. In particular, there was no evidence that administration of CIS led to increased risk of nephrotoxicity, neurotoxicity, increased risk of infections, or increased risk of malignancies. Treatment with CIS was found to be associated with respiratory tract irritation and bronchospasm, but these events were generally mild/moderate, occurred early in patients' treatment course, diminished with time, and were not associated with the development of more serious respiratory complications. These findings were consistent with the analysis of the larger 70 patient safety database.

In March 2005, an open label early access treatment IND was initiated. The purpose of this protocol was to provide CIS to lung transplant physicians for use in suitable lung transplant recipients. Since that time, over 60 lung transplant recipients have received CIS. Data collection is limited to early tolerability subject diaries and serious adverse events (SAEs). Analysis of this safety database has not led to the emergence of any new safety findings. However, in recipients with poor pulmonary reserve (such as those with advanced BOS), intolerance to dosing is more common, and dose titration to the maximal 300 mg dose is sometimes not possible.

The safety and efficacy of CIS in preventing chronic rejection and improving survival in this population of lung transplant patients has been previously demonstrated in a randomized double-blind, placebo-controlled, clinical study.⁽⁸⁾ This study was the basis for a new drug application (NDA) to regulatory authorities. This application received an approvable letter, with approval contingent on additional supporting clinical data. There is currently a multicenter, phase III, randomized, controlled trial designed to assess the efficacy of prophylactic inhaled cyclosporine for the prevention of bronchiolitis obliterans in lung transplant recipients. However, there currently exists limited data on the efficacy of CIS in propylene glycol to treat established BO/BOS occurring in lung transplant recipients and no data in HSCT recipients with established BOS.

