10.4 Stopping Rule

The study will be monitored to ensure that the occurrence of a specified set of treatment related serious adverse events (TRSAEs) during the subsequent weeks (18-70) of intervention does not substantially exceed an anticipated rate. The following TRSAEs will be considered for early stopping of either one of groups A or B:

- Death considered to be probably or definitely related to the inhaled CsA or
- Any grade IV toxicity considered to be probably or definitely related to inhaled CsA, i.e. opportunistic infection such as tissue-invasive CMV or *Pneumocystis carinii*, with exception of temporary cytopenias.

We will monitor the numbers of subjects who have developed any of the above-specified TRSAEs using the stopping rule outlined below. The trial will be seriously considered for early stopping if the number of subjects in the trial who develop TRSAEs is over the pre-specified threshold value in the Table.

From experience using this agent in other clinical settings as detailed in the investigator's brochure, we anticipate the rate of developing at least one of the above-specified TRSAEs to be 10% or less. Following Geller et al., our stopping rule is determined by a Bayesian approach²³. The stopping boundary for the trial is reached if the Bayesian posterior probability that the true probability of developing one or more of the above-specified TRSAEs exceeds this benchmark rate of 10% is at least 90%. We take our prior distribution to be a beta distribution with the sum of the two beta

parameters to be 3, i.e. the parameters of the beta prior distribution are 0.30 and 2.70. Since we have seen in the past that the first few subjects to be accrued are possibly sicker than the rest of the subjects in the sample, we will start safety monitoring when 3 subjects have developed specified SAEs. The following table summarizes the threshold numbers for stopping either group A or B:

Number of Subjects	Stop if the number of subjects who develop any of the number of specified TRSAEs reaches:
≤ 11	3
$12 \leq n \leq 18$	4
$19 \leq n \leq 25$	5
$26 \leq n \leq 32$	6
$33 \leq n \leq 39$	7

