Treatment related SAEs (TRSAEs) are those attributed as possibly, probably or definitely. As detailed in section 10.4 stopping rules, death and any grade IV toxicity considered to be possibly, probably or definitely related to inhaled CIS will be monitored and considered for early stopping the study according to statistically determined criteria.

Hospitalization (overnight admission) for routine supportive care (platelet or RBC transfusions) or admission from the NIH inpatient unit to the NIH ICU for routine monitoring will not be reported as a serious adverse event.

Unanticipated problems that are either AEs or non-AEs, (as defined by Section 12.1 above) will be reported within 7 calendar days of investigator awareness.

All serious adverse events will also be distributed to the Data Safety Monitoring Committee within the same timeframe required for IRB reporting of SAEs.

APT Pharmaceuticals, Inc.: A listing of all SAEs will be submitted to APT pharmaceutical quarterly. Safety reports will be reported as detailed in section 12.5.

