13.3 Risks and Discomforts

13.3.1 Related to Inhaled CIS

CIS is under development for the indication of improved BOS-free survival following lung transplantation. As of November 13, 2009, approximately 444 lung transplant recipients have received CIS under protocols ACS001, ACS002, ACS004, or CIS001. In ACS001, the following adverse events occurred significantly more often in patients receiving CIS than in patients receiving placebo:

- Events that occurred in 30 to 50% of patients receiving CIS: cough, chest pain, back pain, increased urinary frequency, pharyngitis, exacerbation of shortness of breath, and lung consolidation.
- Events that occurred in 10 to 29 % of patients receiving CIS: cardiac murmur, respiratory tract irritation, polyuria, somnolence, hyperlipidemia, respiratory disorder, and hemoptysis.

In the studies that were not placebo controlled, or are as yet unblinded, the following adverse events were seen:

- Events that occurred in greater than 10% of patients: pyrexia, nausea, diarrhea, dyspnea, cough, wheezing, chest pain, pharyngitis, renal impairment, peripheral edema, lung transplant rejection, headache, insomnia, and neutropenia.

- Events that occurred in 5 to 10% of patients: Pharyngolaryngeal pain, pleural effusion, rhinorrhea, constipation, vomiting, fatigue, chest pain, candidiasis, pseudomonas infection, sinusitis, pneumonia, hyperkalemia, leucopenia, anemia, and hypertension.

Although not previously observed, in the initial phase of the NIH study, one subject did develop a rib fracture associated with coughing.

Unknown side effects: In addition, as with other clinical studies using experimental medicines and in subjects with serious medical conditions, there may be adverse events or side effects that are currently unknown and certain of these unknown risks could be permanent, severe, or life threatening. Subjects will therefore be carefully monitored and instructed to seek medical attention in the event of severe adverse events and contact the research team as needed.

Cyclosporine, when taken by mouth can cause kidney damage especially if blood levels are high. So far, use of CIS has not caused this problem in previous human research studies and should not increase this risk since blood levels have been very low.

APT Pharmaceuticals remains attentive to safety throughout all ongoing studies. Additional unexpected safety findings will be provided to investigators upon receipt and evaluation.

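### The causality table in 12.2 steers a new type of grade IV toxicity to 'possibly related', which 10.4 leaves out of the stopping count and 12.3 includes

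*Combined protocol and SAP*

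**What the plan says.** Three places in the combined protocol and SAP bear on this.

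- **12.2, causality table.** The *Probably related* row asks for plausible timing, no ready alternative explanation, and then "The event follows a known pattern of response to the study product. The event decreases with de-challenge". The *Definitely related* row has the same pattern condition and adds recurrence on re-challenge. Only the *Possibly related* row extends the pattern condition, to an "as yet unknown pattern of response"; it does not mention de-challenge. The text above the table tells the investigator to choose the category that fits best overall.
- **10.4, stopping rule.** Two kinds of event enter the count: "Death considered to be probably or definitely related to the inhaled CsA" and "Any grade IV toxicity considered to be probably or definitely related to inhaled CsA" (temporary cytopenias excepted). The 10% benchmark, the threshold table and the simulation all refer back to these events.
- **12.3, event reporting.** "Treatment related SAEs (TRSAEs) are those attributed as possibly, probably or definitely". The section then cites 10.4 and says that "death and any grade IV toxicity considered to be possibly, probably or definitely related to inhaled CIS will be monitored" and considered for early stopping.

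Section 10.4 also has the DSMB evaluate all serious adverse events and allows it to recommend termination for other, unforeseen ones.

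**The concern.** A safety boundary in a long-term extension should be able to register a harm that nobody has described before. The protocol reports "no data in HSCT recipients with established BOS" in 2.6.4 and no long-term data in children in 2.8. In 13.3.1 it warns that "certain of these unknown risks could be permanent, severe, or life threatening". Yet the table treats novelty of pattern as a mark against the two attribution levels that 10.4 counts.

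The evidence that would best implicate the drug is improvement after stopping it. The trial is likely to generate that evidence, because 10.5.2 takes a subject off study drug for a related grade IV toxicity. For an event of unknown pattern, the one row written to receive it gives no weight to that evidence. If 10.4 is applied as printed, such events drop out of the count, and the boundary responds to a lower event rate than the subjects experience.

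**Working it through.** **Step 1: classify the event on the printed text.** Take a grade IV toxicity of a new type with close timing, no other ready cause and improvement off drug.

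| Condition in 12.2 | Possibly | Probably | Definitely |
|---|---|---|---|
| Reasonable timing | met | met | met |
| Not readily explained otherwise | met | met | met |
| Pattern | met (unknown accepted) | not met (known only) | not met (known only) |
| Improves on de-challenge | not asked | met | met |
| Recurs on re-challenge | not asked | not asked | depends on the event |

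The event meets every condition of *Possibly* and three of four for *Probably*. Best fit could go either way, but the only row that names unknown patterns is *Possibly*.

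**Step 2: follow it into the count.** Scored *possibly*, it is outside the 10.4 event definition and inside the 12.3 one.

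**Step 3: reproduce the plan's boundary.** Inputs from 10.4: prior Beta(0.30, 2.70), benchmark 10%, posterior cut-off 90%, monitoring from 3 affected subjects, 39 subjects per group. The threshold at n subjects is the smallest s ≥ 3 with P(p > 0.10 | Beta(0.30 + s, 2.70 + n − s)) ≥ 0.90. This gives 3 for n ≤ 11, 4 for 12–18, 5 for 19–25, 6 for 26–32 and 7 for 33–39, exactly as printed.

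An exact recursion over 39 independent subjects, checking the boundary after each one, gives:

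| Counted event rate | 5% | 10% | 15% | 20% | 30% |
|---|---|---|---|---|---|
| Plan (simulation) | 2.2% | 20.2% | 51.5% | 77.4% | 98.1% |
| Exact | 2.5% | 19.5% | 50.5% | 77.9% | 98.2% |

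Agreement is within 1.0 percentage point. The boundary arithmetic is not in question; what matters is which events enter it.

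**Step 4: size on the strict 10.4 reading.** Let f be the share of true events that are novel, scored *possibly* and not counted. The documents give no value for f, so a range is shown. Counted rate = true rate × (1 − f).

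| True rate | f | Counted rate | Stop probability |
|---|---|---|---|
| 20% | 0 | 20% | 77.9% |
| 20% | 10% | 0.20 × 0.90 = 18% | 68.3% |
| 20% | 25% | 0.20 × 0.75 = 15% | 50.5% |
| 20% | 50% | 0.20 × 0.50 = 10% | 19.5% |
| 30% | 0 | 30% | 98.2% |
| 30% | 25% | 0.30 × 0.75 = 22.5% | 86.8% |
| 30% | 50% | 0.30 × 0.50 = 15% | 50.5% |

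At a true 20% with half the events uncounted, the rule behaves as it does at its 10% benchmark.

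**Step 5: size if 12.3 governs.** *Possibly* related events count, f has no effect, and the f = 0 rows apply.

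**The case against.** A reader might infer that a new toxicity can never reach the stopping boundary. The documents do not support that, for two reasons.

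- Section 12.3 explicitly brings *possibly* related deaths and grade IV toxicities under the 10.4 rule. On that text the causality table has no effect on the count.
- Section 12.2 asks for the best overall fit and does not require every condition in a row. An investigator may score *probably* on timing, absence of another cause and de-challenge.

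Nor is new harm invisible to oversight. The DSMB sees all serious adverse events whatever their attribution and may act on unforeseen ones, and 12.3 to 12.5 provide expedited reporting of unexpected harm. Reaching the boundary prompts only serious consideration of stopping. Much cyclosporine toxicity is already described: 2.6.4 calls the systemic profile well characterized, and the infections that 10.4 gives as examples fall within a known risk. The novel share may therefore be small.

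All of this limits the point without removing it. Best fit still favours the row that names unknown patterns. DSMB discretion has no threshold and no operating characteristics. And 12.3 presents itself as restating 10.4 while using a different attribution threshold, so it cannot settle the matter until the two are reconciled.

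**Conclusion.** The point holds in a limited form. The 12.2 table steers a new type of grade IV toxicity toward *possibly related*, and 10.4 and 12.3 disagree on whether that category enters the stopping count. Under 10.4 as printed the event is missed by the numerical rule; under 12.3 it is counted.

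The loss ranges from nothing (12.3 governs, or investigators score such events *probably*) to a fall from 77.9% to 68.3%, 50.5% or 19.5% at a true 20% rate when 10%, 25% or 50% of events are novel and uncounted. These figures assume independent subjects, a full group of 39, every novel event scored *possibly*, and novel shares that the documents do not supply.

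Section 13.4.1 says that accrual closed as of May 10, 2019 and that only data or sample analysis continues. The present use is therefore mainly in the final safety analysis, not in prospective stopping.

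**What to change.** 1. Reconcile 10.4 with 12.3 so that a single attribution threshold defines the stopping-rule event. If *possibly* related events are included, confirm that the 10% benchmark still describes the acceptable rate of that wider set. It matters: if the wider definition had an acceptable rate of 15% (an assumption), the printed boundary would be crossed 50.5% of the time, against 19.5% at 10%.
2. Add a sentence to 12.2 that an unknown pattern does not by itself rule out *Probably* or *Definitely* when timing, absence of another cause and de-challenge (or re-challenge) point to the drug, and count such events under 10.4. This keeps the pattern condition as evidence without making it a bar. The thresholds need not change for this step.
3. In the final safety analysis, re-examine grade IV events scored *possibly* for an unknown pattern with positive de-challenge or re-challenge, and report the count against the boundary with and without them.

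The cost is a few sentences of text, matching guidance on the case report form, and a short review of the affected records. The downside is slightly more counted events and a slightly higher chance of a DSMB review.

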12.3 Guidelines Event Reporting

Safety Monitoring/Recording/Reporting of Events:

Serious Events

Reports to the IRB and CD:

The PI must report serious UPs, and serious PDs, to the IRB and CD as soon as possible but not more than 7 days after the PI first learns of the event.

Reports to the IRB Chair and CD:

The PI must report all SAEs that do not meet the definition of UP to the IRB chair and CD not more than 14 days after the PI first learns of the event.

Non-serious Events

Reports to the IRB and CD:

The PI must report all UPs that are not serious to the IRB and CD, and PDs that are not serious to the IRB, not more than 14 days after the PI first learns of the event.

Deaths

The PI must report all deaths (that are not UPs) to the CD as soon as possible, but not more than 7 days after the PI first learns of the event.

Reports at the time of continuing IRB review:

At continuing review, the PI will provide to the IRB a summary of:

- All UPs
- All PDs (except for those granted a waiver of reporting)
- All AEs (except for those granted a waiver of reporting)

Clinical adverse events determined directly attributable to the transplant, drugs used in the post-transplant setting, and progression of baseline disease for which the transplant was indicated will not be collected; however these events will be recorded in the patient's medical record.

Adverse laboratory events used to evaluate the safety of this protocol regimen will be collected to include any change from laboratory assessments done prior to first dose of study medication that result in a progression to a grade 3 or 4 laboratory toxicity.

Abnormal labs determined directly attributable to the transplant, drugs used in the post-transplant setting, and/or progression of baseline disease for which the transplant was indicated will not be collected; however these events will be recorded in the patient's medical record.

Only serious and unexpected adverse events related to this protocol will be reported on this ancillary study. Those determined serious and unexpected adverse events related to post transplant complications will be reported on the transplant protocol.

Treatment related SAEs (TRSAEs) are those attributed as possibly, probably or definitely. As detailed in section 10.4 stopping rules, death and any grade IV toxicity considered to be possibly, probably or definitely related to inhaled CIS will be monitored and considered for early stopping the study according to statistically determined criteria.

Hospitalization (overnight admission) for routine supportive care (platelet or RBC transfusions) or admission from the NIH inpatient unit to the NIH ICU for routine monitoring will not be reported as a serious adverse event.

Unanticipated problems that are either AEs or non-AEs, (as defined by Section 12.1 above) will be reported within 7 calendar days of investigator awareness.

All serious adverse events will also be distributed to the Data Safety Monitoring Committee within the same timeframe required for IRB reporting of SAEs.

APT Pharmaceuticals, Inc.: A listing of all SAEs will be submitted to APT pharmaceutical quarterly. Safety reports will be reported as detailed in section 12.5.

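### Section 12.3 does not collect events attributed to the transplant, post-transplant drugs or the underlying disease, and the adverse event table in 10.3 does not carry that restriction

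*Combined protocol and SAP*

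**What the plan says.** Section 12.3 (Guidelines Event Reporting) sets a collection rule that depends on cause. For clinical events judged to result directly from the transplant, it continues: "drugs used in the post-transplant setting, and progression of baseline disease for which the transplant was indicated will not be collected". Such events go into the medical record only. A second sentence, opening "Abnormal labs determined directly attributable to the transplant", applies the same rule and the same three causes to laboratory abnormalities. Between the two, 12.3 describes the laboratory events that are collected, which include "any change from laboratory assessments done prior to first dose of study medication that result in a progression to a grade 3 or 4" toxicity.

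The neighbouring sections do not mention this rule:

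- 12.1 defines an adverse event irrespective of relatedness and says the data go on the CRF.
- 12.2 has the investigator attribute events on a scale that starts at unrelated, a category that covers an established alternative cause.
- 10.3 makes every treated patient evaluable for safety and breaks adverse events down by severity and by transplant group. It has no restriction, label or cross-reference.

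Long-term safety is part of the primary objective (1.1 and 10.1), and the Precis lists the toxicity profile as a secondary endpoint.

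**The concern.** The table planned in 10.3 uses the term that 12.1 defines as all-cause, but it would be filled from data that 12.3 has already filtered by cause. The filter is an investigator's judgement. No blinding is described, and no control arm that could show what the filter removed.

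That judgement is hard to make in these patients. They may take systemic cyclosporine and other immunosuppressants (6.2.4), inhaled cyclosporine is partly absorbed (2.6.4), and the protocol's own toxicity lists for the two routes overlap. An event to which CIS contributed could reasonably be put down to a post-transplant drug and so never reach the table. A reader who is not told of the filter could not tell a low rate of non-serious events from non-collection.

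**Working it through.** The plan gives no figure on this point to reproduce. The check is a comparison of sections, followed by a small illustration.

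**1. Scope.** 12.1 is a general definition; 12.3 is the specific rule for recording and reporting. Giving the specific rule priority, the collected set is all adverse events minus those attributed directly to one of three causes. 10.3 does not say that its table is limited to this set.

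**2. Overlap of toxicities.**

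| Systemic cyclosporine (2.6.4) | CIS (13.3.1) |
|---|---|
| Renal dysfunction | Renal impairment, more than 10% of patients in studies without placebo control or not yet unblinded |
| Headache | Headache, more than 10%, same studies |
| Hypertension | Hypertension, 5 to 10%, same studies |
| Hyperkalemia | Hyperkalemia, 5 to 10%, same studies |
| Dyslipidemia | Hyperlipidemia, 10 to 29% on CIS in ACS001, significantly more often than on placebo |

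So at least one event type that the protocol links to CIS by placebo comparison is also a recognised effect of a drug whose attributed events are not collected.

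**3. What is not lost.**

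- SAEs: 12.3 states that "The PI must report all SAEs that do not meet the definition of UP to the IRB chair and CD" and that "All serious adverse events will also be distributed to the Data Safety Monitoring Committee". It also provides a quarterly listing of all SAEs to the drug supplier.
- Deaths have their own reporting route in 12.3.
- Laboratory values: under Data management in 11.1, NIH results are imported into the trial database and home-physician results are entered. The values therefore exist whether or not a change was coded as an adverse event.

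What remains exposed is non-serious clinical events and the adverse event coding of laboratory changes.

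**4. Direction.** Omission can only lower an all-cause count. It lowers a count of CIS toxicity only where the attribution was wrong.

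**5. Weight of one omission (not an estimate of bias).** Inputs: at most 39 subjects per group (study summary) and 78 in total (10.2). Actual enrolment is not given, so n = 20 is shown as an assumed alternative. The exact two-sided 95% upper limit for x of n is the 97.5th percentile of Beta(x + 1, n − x).

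| n | One subject | Upper limit at 0/n | Upper limit at 1/n |
|---|---|---|---|
| 39 | 1/39 = 2.6 points | 1 − 0.025^(1/39) = 9.0% | Beta(2, 38): 13.5% |
| 20 (assumed) | 1/20 = 5.0 points | 1 − 0.025^(1/20) = 16.8% | Beta(2, 19): 24.9% |

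The documents do not give the number of subjects affected.

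**The case against.** The strongest reply is that the exclusion is deliberate, openly stated and sensible. Transplant recipients have many background events, and without a comparator all-cause counts overstate drug toxicity. If an event was correctly attributed to the transplant, leaving it out gives the right count for CIS. The Precis wording about events associated with extended CIS treatment fits that intent. The attribution scale in 12.2 keeps its use, because unrelated events from any other cause are still collected. Section 2.6.4 reports no evidence of added nephrotoxicity, and 2.8 puts systemic exposure about 7-fold below oral dosing at comparable doses, so few events may be affected.

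Much of this stands. It disposes of the claim that 12.1 and 12.3 flatly contradict each other, and it shows that a table misread as all-cause is an inference, since 10.3 gives no table shell or title. It does not supply the missing restriction in 10.3, and it relies on attribution being right where the toxicity lists overlap.

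A reader might infer more, but the documents do not support it:

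- *That serious events are lost too*, from "Only serious and unexpected adverse events related to this protocol will be reported on this ancillary study" and "Those determined serious and unexpected adverse events related to post transplant complications will be reported on the transplant protocol". Those sentences concern which protocol reports an event, and the all-SAE routes stand beside them.
- *That the promise to the IRB of "All AEs (except for those granted a waiver of reporting" is broken.* That sentence allows waivers, and whether one covers these events would be in IRB records not available here.
- *That the stopping rule in 10.4 is weakened.* It counts deaths and grade IV toxicities already attributed to inhaled cyclosporine. Misattribution would affect that count with or without the collection rule.

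**Conclusion.** The point holds as a reporting gap that should be fixed. 12.3 filters collection by attributed cause, and 10.3 neither applies nor discloses the filter. The loss is confined mainly to non-serious clinical events and to whether laboratory changes are coded as adverse events. Relative to an all-cause count it is downward only, and its size cannot be derived. The 2.6 points, and the upper limit of 9.0% instead of 13.5%, show only what one omitted subject would weigh at the maximum group size.

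This rests on two assumptions: that 12.3 was followed as written, and that the 10.3 table is drawn from the adverse events collected under it. It does not show that CIS toxicity was under-reported, and the exclusion is stated openly in the protocol.

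**What to change.** Section 13.4.1 says the study is closed to accrual and in data or sample analysis only, so changing what is collected would come too late. Amend 10.3 instead:

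1. Tabulate laboratory shifts to grade 3 or 4 from pre-first-dose values, as 12.3 defines them, without regard to attribution. Use the NIH and home-physician results already in the database. Subjects enter already on CIS, so state which first dose sets the baseline.
2. Show all SAEs and deaths by group, with all-cause and treatment-related counts side by side.
3. Cross-refer 10.3 to 12.3. Label the clinical adverse event table as excluding non-serious events attributed to the transplant, post-transplant drugs or progression of the transplant-indicating disease, and report this as a limitation.

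The cost is a little more analysis on data already held, plus IRB approval of the amendment (11.1). No new visits or tests are needed. Reported rates may look less favourable. All-cause counts without a comparator do not isolate CIS toxicity, which is why the treatment-related column stays beside them.
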